## 2.0 Add Department(s)

2.1 List departments associated with this study. If the study is funded, please associate it with the correct A&M System member.:

Primary Dept?	Department Name
	TAMU - College of Liberal Arts - Psychology
	TAMU - TAMU - Psychology
	TAMU - Texas A&M University - Not Specified

**4.0**

**Request to the Human Research Protection Program :: Please Select **ONE** of the options below.**

**Version 03.30.2021**

**4.1 I am conducting Human Subjects Research, and I want to proceed to the regular application.**

Yes  No

Which IRB reviews your research?

TAMU IRB  
 Dentistry IRB

**4.2 I am requesting a determination - is my project human subjects research?**

Yes  No

**4.3 I am requesting a determination to see if my research falls into an EXEMPTION category.**

Yes  No

**4.4 I am requesting to defer to an external IRB (that is not IRB TAMU or IRB Dentistry).**

Yes  No

**4.5 I am requesting a "Delayed Onset" of human subjects research determination.**

Yes  No

**6.0****Texas A&M University Human Research Protection Program**

## Project Application Form

### Study Introduction

#### 6.1 Application Checklist

The following checklist is a guide for researchers regarding supporting documents that must be considered for and/or uploaded with this application for review and approval before use.

- Informed Consent Document
- Information Sheet
- Waiver of HIPAA Authorization
- Parental Permission Form/Minor Assent Form
- Recruitment materials (i.e. flyers, emails, advertisements, telephone scripts, social media posts)
- Site Authorization Letter (for study conduct and/or access to administrative records)
- Survey/Questionnaire/Data Collection/Abstraction Forms
- Grant Applications (cover to cover), required if funded or grant submitted
- Instructions
- Protocol Investigator's Brochure (for clinical trials only)
- Case report form (for clinical trials only)
- Device Manual (if using an approved or investigational device)
- Thesis/dissertation proposal
- Waiver of parental permission/minor assent form
- Letter of cultural evaluation for international research (link to SOP)
- IRB approvals from collaborating institutions
- Any other documents related to the research
- CVs for all investigators when proposed activities are more than minimal risk
- CITI training for all personnel

#### 6.2 Proprietary Information

This protocol includes confidential and/or proprietary information to be protected from disclosure.

Yes  No

#### 6.3 Is this research funded?

Please identify your funding source, if applicable.

View Details	Sponsor Name	Sponsor Type	Funding Through	Contract Type:	Project Number	Award Number
No Sponsor has been added to this Study						

Please provide the name of the PI on the funding/grant if it is different from this IRB application.

Will funds from Qatar be used to fund this research?

Yes  No

**\* If the response to this question is Yes, then approval by an IRB in Qatar may also be required.**

#### 6.4 Has an entity conducted a scientific peer-review of this research?

Yes  No

If Yes, please specify:

## 6.5 Fee for Service Information

Is a company providing contract services associated with this research in which no company personnel are considered collaborators in the research (will not receive professional recognition or included in presentations or publications about the research)?

Yes  No

If yes, please provide the name of the company and the contact name.

If a contract exists for this study, was the fee for service information included in the primary award information?

Yes  No

If yes, please provide a copy of the contract.

Version	Title	Category	Expiration Date	Document Outcome	Checked Out	View Document
No Document(s) have been attached to this form.						

## 6.6 Is this project part of a dissertation, thesis, or record of study?

Yes  No

If available, please attach the proposal under Other Study Documents at the conclusion of the application. If not yet available, submit it as an amendment form when available.

## 7.0 Study Scope

### 7.1 Research Classification

Select all that apply:

- Social/Behavioral
- Biomedical
- Both
- Clinical Trial
- Other, specify

For Social/Behavioral Research, select all that apply.

- Questionnaire/Survey
- Observation (investigator observing participants)
- Retrospective study of records existing at time of this application
- Exposure to some type of stimulus or intervention (includes device or substance)
- Participant observation (investigator acts as participant)
- Interview
- Focus Group
- Other, specify

## 7.2 Vulnerable Populations

Identify any vulnerable populations that will be included in the study:

- Children (for example, in Texas, under 18)
- Pregnant women, human fetuses, neonates
- Individuals with physical disabilities
- Individuals with cognitive disabilities
- Economically or educationally disadvantaged persons
- Prisoners
- Other (for example, individuals with psychiatric disorders, emotional/social impairments, depression, etc.)
- No Vulnerable Populations will be included.

If Other, then please explain:

Describe additional safeguards planned to protect the rights and welfare of vulnerable subjects:

If a subject transitions into one of the vulnerable populations (pregnant women or cognitively impaired), will the study procedures place them at any additional risk?

Yes  No

If a subject becomes incarcerated (including awaiting sentencing, court-mandated treatment, or in prison), contact the IRB immediately.

Please justify the use of vulnerable/special populations.

## 8.0

## Project Overview - Protocol Section Begins Here

### 8.1 Project Summary

In the space below, provide a summary of the project. Include information about background and rationale for the study including preliminary data, purpose, objectives, specific aims, and research questions. Character limit: 5,000 (applies to first box).

#### Background

Individuals often think of how a situation or outcome could have turned out differently -- if only something was different or something had changed, then the outcome could have been better or worse. This is a common type of thinking, known as counterfactual thinking, that often takes the form of "if only" statements. These thoughts are frequent after negative events, but have also been found to occur after positive events and 'near misses'. Research has shown that their evaluative nature elicits a variety of consequences, such as biased decision making, changes in an event's meaningfulness, heightened positive or negative affect, and future behavioral changes (such as intentions, motivation, persistence/effort; for review, see: Epstude & Roese, 2008; Roese & Epstude, 2017). Specifically, many areas of research involving counterfactuals have often looked into key elements that are often discussed in other health behavior literature, such as self-efficacy, motivation, and intentions (Tal-Or, Boninger, & Gleicher, 2004; Wong, 2007; Smallman & Roese, 2009). One such area that incorporates these elements is health promotion literature, such as Protective Behavioral Strategies (PBS) and alcohol consumption

(Dvork, Pearson, Neighbors, Martens, & Stevenson, 2016; Dvorak, Pearson, Neighbors, & Martens, 2015). The objectives of this study are laid out as such: First, to further explore the role counterfactuals play in increasing an individual's intentions toward behavioral change. Second, to further elucidate the inner and outer workings of Protective Behavioral Strategies for increasing positive health behaviors. Finally, to address the applicability of a counterfactual intervention on promoting intentions to use PBS.

### **Procedure**

All data will be collected on qualtrics. Interested individuals will sign up using the online subject pool, SONA. Part 1 will be completed online, either in the lab or at their own personal computer. After electronically confirming consent (using the provided informed consent sheet from TAMU Research Compliance and Biosafety), participants will complete demographics, followed by the Alcohol Use Disorder Identification Test, a measure of perceived behavioral control, a measure of delay-discounting, the Daily Drinking Questionnaire-Revised, the Young Adult Alcohol Consequences Questionnaire, Protective Behavioral Strategies (PBS), the Personal Assessment of Responsible Drinker Identity Scale, Alcohol Use Contemplation/Intention measure. After these measures have been completed, participants will then be randomly assigned to one of four conditions. In one condition, participants will be asked to only write about a negative drinking event. In the second condition, participants will be asked to write about a negative drinking event in addition to recalling facts about the same event. In the third condition, participants will be asked to write about a negative drinking event and will then complete a counterfactual task. The task will ask the individuals to list three counterfactual strategies about the negative event, future situations these strategies could be used, as well as obstacles to using the strategies. The task will wrap up by asking these participants to indicate intention to use those strategies in the future. In the fourth condition, participants will be asked to complete the Personalized Normative Feedback (PNF). Participants in all conditions will complete perceptions of protective behavioral strategy norms questions, the Alcohol Use Contemplation/Intentions measure, a measure of perceived behavioral control as well as intentions to use protective behavioral strategies.

All follow up parts will be either online or in the lab, one week apart. Participants will indicate, for each day the previous week (Sunday, Saturday, Friday, Thursday, Wednesday, Tuesday, Monday), what they were doing, their general location, if they consumed alcohol that day, and the extent to which they experienced a list of situations. Following this, all participants will then indicate the extent that they used the list of PBS. For those who had been randomly assigned to the counterfactual condition in Part 1, they will complete additional measures: indicating the use of the counterfactual strategies that the participant came up with in Part 1 and their intention to use these counterfactual strategies over the next week. Finally, all participants will complete a measure of perceived behavioral control, rate intentions to use PBS in the next week, and answer the protective behavioral strategy norms questions. In follow up sessions 4 and 6, participants will also complete the Personal Assessment of Responsible Drinker Identity Scale and the delay discounting task. Email information will be completed at the end of each part. A page displaying additional resources will also be displayed. All participants will finish the study by completing a debriefing task after the final follow up.

### **Procedures Involved:**

**In the space below, Describe and explain the study design. Provide a description of all research procedures being performed and when they are performed.**

**List each procedure or test and how often the procedure or test will occur for each participant.**

**Include a procedure schedule or table of events, if applicable - clinical studies.**

**Describe: All source records that will be used to collect data about subjects. This includes surveys, scripts, recordings and data collection forms; all test articles including dietary supplements, drugs and devices used in the research and the purpose of their use, and their regulatory (FDA) approval status.**

---

Responses will be recorded through the survey website Qualtrics. Once data collection has concluded, responses will be downloaded onto an Excel sheet and stored on a password-protected computer.

See attached for exact questions in each measure. descriptions of each task are below.

Prescreen (through Psychology Subject Pool)

AUDIT

Baseline Part 1

**Pre-manipulation measures:**

Task 1: Demographics

Task 2: AUDIT

Task 3: DDQ-R

Task 4: Perceived Behavioral Control

Task 5: Delay Discounting Measure

Task 6: YAACQ

Task 7: PBS-20

Task 8: PARDI

Task 9: Alcohol Use contemplation/intention measure

**Manipulation**

Condition 1: Negative event only

Condition 2: Negative event and Fact listing

Condition 3: Negative event and counterfactual task

Condition 4: Personalized Normative Feedback

**Post-manipulation measures**

Task 9: Perceived behavioral control

Task 10: PBS Intentions

Task 11: Perceptions of Protective Behavioral Strategies questions

Task 12: Alcohol Use contemplation/intention measure

Task 13: Email

Task 14: Additional Resources

Follow Up Parts 2-6

Task 1:PBS-20

Task 2: Daily indication of drinking and strategy use

Task 3: Counterfactual Behavior Use and Intentions

Task 4: Perceived behavioral control

Task 5: PBS Intentions

Task 6: Perceptions of Protective Behavioral Strategies questions

Task 7: PARDI [only follow up sessions 4 and 6]

Task 8: Delay Discounting Measure [only follow up sessions 4 and 6]

Task 9: Email

Task 10: Additional Resources

(End of Part 6): Debriefing

**Demographics.** A basic demographics questionnaire will collect data on participants' age, gender, ethnicity, race, language spoken, and fluency in English.

**Alcohol Use Disorder Identification Test** (AUDIT; Saunders, Aasland, Babor, De La Fuente, & Grant, 1993). Participants will complete the Alcohol Use Disorder Identification Test – Consumption Scale (AUDIT-C), which is a screener for alcohol consumption. Previous studies support the reliability and validity of the AUDIT-C as a measure of alcohol consumption among college students (DeMartini & Carey, 2012).

**Daily Drinking Questionnaire-Revised** (DDQ-R; adapted from Collins, Parks, & Marlatt, 1985) Assesses drinking habits and patterns among individuals averaged over the last 3 months.

**Perceived Behavioral Control.** (PBC; Cooke, Sniehotta, & Schuz, 2007; Ajzen & Sheikh, 2013) This measure is on a 7-point scale and is composed of six items: For me to avoid drinking alcohol is (difficult-easy); I am confident that, if I wanted to, I could avoid alcohol (definitely false-definitely true); How much control do you believe you have over avoiding alcohol (no control- complete control)? For me to drink less than 7(females)/10 (males) units in a single session in the next week would be (very difficult-very easy). If I wanted to I could drink less than 7(females)/10(males) units in a single session in the next week (definitely false-definitely true). How much control do you believe you have over drinking less than 7(females)/10(males) units in a single session in the next week? (no control-complete control).

**Delay Discounting.** Delay discounting will be assessed utilizing an adjusting-delay task developed by Bickel & Colleagues (see Epstein et al., 2014 for description). Participants are presented with items prompting a choice between receiving a certain amount of money (\$1000) after a specified delay (i.e., 1 day, 1 week, 1 month, 3 months, 1 year, 5 years, or 25 years) or receiving a smaller amount of money immediately. The value of the

immediate reward is adjusted across trials by using a decreasing-adjustment algorithm. This procedure determines the point at which participants are indifferent to the difference between the smaller, immediate reward and the larger, delayed reward. An area under the curve (AUC) procedure, as specified by Myerson, Green & Warusawitharana (2001) is used to characterize data from the discounting task. From the AUC, smaller values indicate greater monetary discounting by delay and greater impulsivity. K-values are also calculated.

**Young Adult Alcohol Consequences Questionnaire** (YAACQ; Read, Kahler, Strong, & Colder, 2006). The YAACQ contains 48-items that assess alcohol-related consequences.

**Protective Behavioral Strategies** (PBS-20; (Treloar, Martens, & McCarthy, 2015) Protective Behavioral Strategies (PBS) are specific behaviors one can utilize to minimize the harmful consequences of alcohol consumption. There are three types of PBS: Serious Harm Reduction, Limiting/Stopping Drinking, and Manner of Drinking.

**Personal Assessment of Responsible Drinker Identity Scale:** A scale measure that assess how much being a responsible drinker is part of your identity

**Perceptions of Protective Behavioral Strategies Questions:** Questions about the percentage and frequency of use of protective behavioral strategies among college students.

**Drinking Contemplation/Intention Measure:** A measure assessing how much an individual is considering changing their drinking behavior

**Negative Event Only (Condition 1).** Participants will be asked to think of a specific example of the most (or one of the most) negative, unpleasant event with alcohol they have experienced; the event they choose must have occurred at least a year ago. Or they will be asked to think of the most significant event that has occurred in the past year. After thinking of a specific event, they will be given three minutes to write about their experience. The writing prompt will ask that they express the event information in a few sentences. This writing prompt will help participants place themselves back into that moment and access salient emotions and cognition about it. Similar negative event prompts have been used in counterfactual thinking studies (McFarland & Alvaro, 2000; White & Lehman, 2005).

**Negative Event + Factual Thinking Task (Condition 2).** Participants in this group, the event plus the factual thinking task condition, will be told the following after completing the negative event writing task, "After disappointing and/or negative experiences like the one you described on the previous page, people often think about the details of the situation. For example, when it happened, who was involved, and what happened right before or after the incident occurred. In the space below please provide examples of some of these details.." There will be 10 blank boxes below the instructions and participants will be asked to provide some examples of details from their traumatic event. They will be asked to only list as many as they can naturally recall without repeating any. This procedure is derived from Kray and colleague's (2010) study on counterfactual thinking and meaning in life.

**Negative Event + Counterfactual Task (Condition 3).** Participants in this group, the event plus the counterfactual task condition, will be told the following after completing the negative event writing task, "After disappointing and/or negative experiences like the one you described on the previous page, people sometimes cannot help thinking "what if..." or "if only..." and imagining how things might have gone differently. That is, if only I had done something differently, the negative drinking situation could have been avoided or turned out better than it did. In the box below please identify things that, had they been different, would have improved the outcome of the negative drinking situation you described earlier and briefly describe how the outcome would have been better." There will be 3 blank boxes below the instructions and participants will be asked to list three counterfactuals about the event they just described. They will be asked to only list as many as they can naturally recall without repeating any. After writing out their counterfactual thoughts, these participants will be asked to think of situations where these strategies could be used. Participants will also be asked to list out any obstacles that might prevent them from implementing these strategies. Lastly, participants in this condition will indicate their intention to use each strategy over the next week.

**Personalized Normative Feedback (Condition 4).** Participants in this group, the personalized normative feedback, will be asked to rate the frequency and quantity of TAMU students that use PBS when drinking.

**Perceived Behavioral Control.** (PBC; Cooke, Sniehotta, & Schuz, 2007; Ajzen & Sheikh, 2013) This measure is on a 7-point scale and is composed of six items: For me to avoid drinking alcohol is (difficult-easy); I am confident that, if I wanted to, I could avoid alcohol (definitely false-definitely true); How much control do you believe you have over avoiding alcohol (no control- complete control)? For me to drink less than 7(females)/10 (males) units in a single session in the next week would be (very difficult-very easy).If I wanted to I could drink less than 7(females)/10(males) units in a single session in the next week (definitely false-definitely true). How much control do you believe you have over drinking less than 7(females)/10(males) units in a single session in the next week? (no control-complete control).

### **Protective Behavioral Strategies Intentions** (adapted from Treloar, Martens, & McCarthy, 2015).

Intentions to use protective behavioral strategies was adapted from the Protective Behavioral Strategies Scale -20. All participants will be asked how much they intend to use PBS in the next week when/if they drink, for each PBS subtype. Responses fall on a 6-point Likert-type scale of Never (1), Rarely (2), Occasionally (3), Sometimes (4), Usually (5), Always (6), and Do not wish to respond.

#### **Email**

Please enter your TAMU email ([contact]) so we can contact you for future follow phases of the study if you qualify. Remember, everything you reported here is completely confidential. (free text)

## **Parts 2-6**

**PBS-20:** Participants will be asked to indicate for each day of the previous week how often they used the three types of PBS (Serious harm reduction, limiting/stopping, and manner of drinking). Participants will also be asked to indicate how effective they believe each type of strategy is.

**Weekly Indication of Drinking and Strategy Use:** During each follow up, participants will indicate, for each day the previous week (Sunday, Saturday, Friday, Thursday, Wednesday, Tuesday, Monday)), what they were doing, their general location, and if they consumed alcohol that day.

**Counterfactual Behavior Use and Intentions:** Participants in the counterfactual condition will reread their counterfactuals that they wrote in the baseline session. They will answer questions about whether they did those behaviors in the past week and their intentions to use those behaviors in the next week.

**Perceived Behavioral Control.** (PBC; Cooke, Snihotta, & Schuz, 2007; Ajzen & Sheikh, 2013) This measure is on a 7-point scale and is composed of six items: For me to avoid drinking alcohol is (difficult-easy); I am confident that, if I wanted to, I could avoid alcohol (definitely false-definitely true); How much control do you believe you have over avoiding alcohol (no control- complete control)? For me to drink less than 7(females)/10(males) units in a single session in the next week would be (*very difficult-very easy*). If I wanted to I could drink less than 7 (females)/10(males) units in a single session in the next week (*definitely false-definitely true*). How much control do you believe you have over drinking less than 7(females)/10(males) units in a single session in the next week? (*no control-complete control*).

**Intentions:** (adapted from Treloar, Martens, & McCarthy, 2015). Intentions to use protective behavioral strategies was adapted from the Protective Behavioral Strategies Scale -20. All participants will be asked how much they intend to use PBS in the next week when/if they drink, for each PBS subtype. Responses fall on a 6-point Likert-type scale of Never (1), Rarely (2), Occasionally (3), Sometimes (4), Usually (5), Always (6), and Do not wish to respond.

**Personal Assessment of Responsible Drinker Identity Scale [follow up 4 and 6 only]:** A scale measure that assess how much being a responsible drinker is part of your identity

**Perceptions of Protective Behavioral Strategies Questions:** Questions about the percentage and frequency of use of protective behavioral strategies among college students.

**Delay Discounting [follow up 4 and 6 only].** Delay discounting will be assessed utilizing an adjusting-delay task developed by Bickel & Colleagues (see Epstein et al., 2014 for description). Participants are presented with items prompting a choice between receiving a certain amount of money (\$1000) after a specified delay (i.e., 1 day, 1 week, 1 month, 3 months, 1 year, 5 years, or 25 years) or receiving a smaller amount of money immediately. The value of the immediate reward is adjusted across trials by using a decreasing-adjustment algorithm. This procedure determines the point at which participants are indifferent to the difference between the smaller, immediate reward and the larger, delayed reward. An area under the curve (AUC) procedure, as specified by Myerson, Green & Warusawitharana (2001) is used to characterize data from the discounting task. From the AUC, smaller values indicate greater monetary discounting by delay and greater impulsivity. K-values are also calculated.

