#### 9.6 Experience of Subjects

Describe the experience of subjects while participating in this research. (Please describe what the participant will experience from the time of learning of the study through completion.)

Participants (undergraduate students at TAMU who need to participate in research for class credit) will sign up to participate in the study by using the SONA subject participation pool. After signing up for Part 1, online participants will receive a link to a Qualtrics survey. Those who are completing the study in lab will participate on the day they signed up for. After reading information about the study and consenting electronically by clicking "I agree", participants will report their TAMU email and then continue on to complete the Part 1 questionnaires. This should take 30 minutes of their time and they will receive 1 credit toward their class research requirement for completing Part 1.

After completing Part 1, participants will be allowed to participate in the follow up sessions (parts 2-6) if they correctly and completely fulfilled the writing task requirements. Each follow up session will be completed through Qualtrics and should not exceed 30 minutes for each follow up session. Each follow up session will take place one week after the previous session. A summary of this is below:

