**Part 1: Baseline**

**Part 2: First follow up (One week after baseline)**

**Part 3: Second follow up (One week after Part 2)**

**Part 4: Third follow up (One week after Part 3)**

**Part 5: Fourth follow up (One week after Part 4)**

**Part 6: Fifth follow up (One week after Part 5)**

*Note: If there is not enough time in the semester, some participants may not complete all follow-ups; they will complete the number of sessions and follow ups described in their consent forms*

How long will the participants be engaged in the research (length of time, e.g., 15 minutes, 45 minutes on Day 1, 60 minutes on Day 2, etc.)?

30 minutes for Part 1 (week 1)  
30 minutes for Part 2 (week 2)  
30 minutes for Part 3 (week 3)  
30 minutes for Part 4 (week 4)  
30 minutes for Part 5 (week 5)  
30 minutes for Part 6 (week 6)

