**18.6 Have the PI, Co-I(s), and any persons interacting with study subjects completed CITI training?**

Yes  No

If No is selected, have the PI, Co-I(s), and any persons interacting with study subjects completed alternative human subjects training? If so, please provide a description and copy of the alternative training.

**18.7 Please indicate the research personnel who will be obtaining informed consent from participants. (Use N/A to indicate that informed consent will not be collected.)**

N/A

**18.8 What project-specific training/experience have individuals obtaining informed consent received (e.g. verbal instruction by the PI, practice with the PI)?**

N/A

**18.9 Will the subject have the opportunity to review the informed consent document or Information Sheet, ask questions, and understand the details of the study prior to participation?**

Yes  No

If Yes, then how much time will be provided?

However much time participants choose to take. Participants first have the opportunity to review the information sheet during Part 1 of the study which is completely online and completed wherever and whenever the participant chooses.

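### The follow-up recall week is not anchored to the session date or to Part 1; if it means the last calendar week, Part 2 takes in 0 to 6 full days from before randomisation

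*Protocol*

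**What the plan says.** Protocol section 8.1, under Parts 2-6, has participants report their activity, location and drinking "for each day the previous week (Sunday, Saturday, Friday, Thursday, Wednesday, Tuesday, Monday". The list runs back from Sunday to Monday there and in both copies of the Procedure text. For the PBS-20, "Participants will be asked to indicate for each day of the previous week how often they used the three types of PBS". Participants in the counterfactual arm also report on their own strategies: "They will answer questions about whether they did those behaviors in the past week". None of these windows is given a start or end date.

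On timing, the Procedure says "All follow up parts will be either online or in the lab, one week apart", and section 9.6 lists "Part 2: First follow up (One week after baseline". Randomisation and the writing task both fall within Part 1, after the baseline measures. For the day of Part 1, section 9.6 says "Those who are completing the study in lab will participate on the day they signed up for". Section 18.9 describes Part 1 as "completely online and completed wherever and whenever the participant chooses". No section fixes a weekday for any session.

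The SAP (Statistical Design, Covariates) analyses only weeks with drinking and adjusts for study week, number of drinking days and sex. It has no rule for reported days that precede Part 1.

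**The concern.** A list that runs back from Sunday to Monday reads most naturally as the last completed calendar week. That week matches the seven days since the previous session only when sessions fall on a Monday. For any other start day, part of the week reported at Part 2 would lie before randomisation.

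Such days cannot carry an effect of the assigned condition. They would nevertheless enter the weekly PBS and drinking values as post-intervention outcome. They would also help decide whether Part 2 counts as a drinking week: a participant who stopped drinking after the task could still be kept in the analysis because of earlier drinking.

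For superiority over control (path a, then H2 and H3), the result is dilution. For the non-inferiority clause in Hypothesis 1 and the exploratory equivalence test, dilution works the other way, because it makes the counterfactual and PNF arms look more alike.

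**Working it through.** The documents give no figure for this point, so there is nothing to reproduce. The check is a count of days.

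**Inputs.** Part 1 falls on a weekday that is k days after Monday (k = 0 to 6). Part 2 falls exactly seven days later (section 9.6). There are five follow-ups (Parts 2-6), or three or four in late-semester waves: section 15.2 describes four- and five-week participation, one session of which is Part 1.

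**Reading A: the last completed Monday-to-Sunday week.** At Part 2 this is the calendar week that contains Part 1. Full days before Part 1 = k, the Part 1 day itself = 1, full days after = 6 − k.

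| Part 1 day | Full days before | Part 1 day | Full days after |
|---|---|---|---|
| Monday | 0 | 1 | 6 |
| Tuesday | 1 | 1 | 5 |
| Wednesday | 2 | 1 | 4 |
| Thursday | 3 | 1 | 3 |
| Friday | 4 | 1 | 2 |
| Saturday | 5 | 1 | 1 |
| Sunday | 6 | 1 | 0 |

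The documents give no distribution of start days, so any average is an assumption. Spread evenly over Monday to Friday, mean k = (0+1+2+3+4)/5 = 2, or 2/7 = 29% of Part 2. Spread evenly over seven days, mean k = 21/7 = 3, or 3/7 = 43%.

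The share of all follow-up days is k/(7F), where F is the number of follow-ups and every week is kept with equal weight:

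| F | Mean k = 2 | Mean k = 3 | Range, k = 0 to 6 |
|---|---|---|---|
| 5 | 2/35 = 5.7% | 3/35 = 8.6% | 0 to 17.1% |
| 4 | 2/28 = 7.1% | 3/28 = 10.7% | 0 to 21.4% |
| 3 | 2/21 = 9.5% | 3/21 = 14.3% | 0 to 28.6% |

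**Reading B: the seven days before the session.** At Part 2 the window starts on the Part 1 day. Full days before Part 1 = 0 for every weekday; only the Part 1 day straddles randomisation.

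**What dilution of this size could do, under reading A.** This is an illustration only. Assume a true d of 0.20, 1500/4 = 375 per arm, two-sided 5%, no attrition, independent participant means, unchanged SD, and an effect that shrinks in proportion to the share of pre-randomisation days. At 8.6%, d becomes 0.20 × (1 − 0.086) = 0.183 and power falls from 78.2% to 70.6%. At 14.3%, d becomes 0.20 × (1 − 0.143) = 0.171 and power falls to 65.1%. With an assumed d of 0.30 the fall is smaller: 98.4% to 96.4% and 94.1%.

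For the equivalence margin of ±0.20, a true counterfactual-PNF difference of up to 0.20/(1 − 0.086) = 0.22, or 0.20/(1 − 0.143) = 0.23, would shrink to within the margin.

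**The case against.** The strongest objection is that the calendar week is an inference. Any seven-day window contains the seven named days, sessions are a week apart, and the counterfactual items speak of the past week. All of this fits a rolling window, under which no full day precedes Part 1. Section 8.1 refers to an attachment for the exact items, and that attachment is not among the documents. The screen may already show dates. This stands. A reader might infer that Part 2 certainly counts pre-randomisation days as outcome, and the documents do not support that. They show only that the window is undefined and that the listed order leans towards the calendar reading.

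A reader might also infer a bias in favour of one arm. Randomisation makes the overlap equal across arms in expectation, and it can arise only at Part 2. It is conservative for superiority and H2-H3. It favours similarity only in the non-inferiority clause of H1 and in an equivalence test that is labelled exploratory.

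A third tempting inference is that 29-43% of some participants' data is affected. That would need Part 2 to be the only week analysed. The Participants text in section 8.1 requires completion of all parts for inclusion, so such a record could arise only if the drinking-week filter removed every other week.

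Three smaller points also stand. The section 18.9 wording answers a question about time to read the consent information and is not a scheduling rule; still, nothing else fixes a weekday. The overlap vanishes for Monday starts, or if Part 2 slips into a later calendar week. Finally, Friday can be a pre-randomisation day only for Saturday or Sunday starts, and Saturday only for Sunday starts. If drinking is concentrated on those two days (an assumption), the day counts overstate the dilution for Monday-to-Friday starts.

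**Conclusion.** The concern holds in conditional form. The protocol does not define the recall window relative to the session or to Part 1, and the SAP has no rule that keeps the first outcome week after randomisation. If the window is the last calendar week, Part 2 contains 0 to 6 full pre-randomisation days out of 7. On average that is about 6-9% of follow-up days with five follow-ups and 10-14% with three. These averages assume start days spread evenly over five or seven days, Part 2 exactly one week after Part 1, and equal weight for each week. If the window is the last seven days, the figure is zero full days.

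The consequence is dilution confined to one follow-up and equal in expectation across arms, plus possible misclassification of Part 2 as a drinking week. It does not invalidate the randomised comparison. It is worth correcting because it lies in the outcome definition, is cheap to remove, and works in the permissive direction for the comparison with PNF. This is a moderate point rather than a critical one.

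**What to change.** In Parts 2-6, have the survey show dated days that cover the period since the previous session, for both the drinking grid and the PBS-20 grid, with no date before Part 1. State this window in the protocol. If the attached items already show dated days, saying so there closes that part of the point.

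In the SAP, state that Part 2 days before Part 1 are dropped, and how the Part 1 day itself is treated, before weekly PBS, drinks and drinking-week indicators are built.

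For data already collected on an undated fixed grid, apply the same rule wherever day-level records exist. The Parts 2-6 text describes daily PBS reports, but the Procedure mentions only the extent of use, so it needs checking whether PBS was stored by day. Where it was not, run a sensitivity analysis without Part 2.

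The cost is a display change in the follow-up surveys and a short SAP addition. The downside is that some Part 2 records will rest on fewer than seven days; omitting Part 2 in the sensitivity analysis also loses one follow-up.
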